8 SAFETY AND ADVERSE EVENTS.....	10
8.1 DEFINITIONS.....	10
8.2 RECORDING OF ADVERSE DEVICE EFFECTS.....	11

8.3 REPORTING OF ADVERSE DEVICE EFFECTS AND UNANTICIPATED PROBLEMS	11
8.3.2 Investigator reporting: Notifying the IRB	12
8.4 STOPPING RULES	13
8.5 MEDICAL MONITORING	13
8.5.1 Data Monitoring Committee	14
9 DATA HANDLING AND RECORD KEEPING	14
9.1 CONFIDENTIALITY	14
9.2 SOURCE DOCUMENTS	15
9.3 CASE REPORT FORMS	15
9.4 RECORDS RETENTION.....	15
10 STUDY MONITORING, AUDITING, AND INSPECTING.....	15
10.1 STUDY MONITORING PLAN	15
10.2 AUDITING AND INSPECTING.....	15
11 ETHICAL CONSIDERATIONS.....	16
12. STUDY FINANCES	16
12.1 FUNDING SOURCE	16
12.2 CONFLICT OF INTEREST.....	16
13 PUBLICATION PLAN	16
14 REFERENCES	17

List of Abbreviations

ADM – abductor digiti minimi

APB – abductor pollicis brevis

DCS – direct cortical stimulation

EEG – electroencephalography

EMG – electroencephalography

MEP – motor evoked potential

nTMS – navigated transcranial magnetic stimulation.

TMS – transcranial magnetic stimulation.

rMT – resting motor threshold

Study Summary

Title	Validation of Presurgical Motor Mapping with Transcranial Magnetic Stimulation (TMS) in patients with Epilepsy
Protocol Number	
Methodology	Open label phase 1 trial
Study Duration	2 years
Study Center(s)	NYU Langone Medical Center NYU Comprehensive Epilepsy Center
Objectives	To examine the degree of concordance between presurgical neuronavigation guided TMS (nTMS) and direct cortical stimulation (DCS) in identifying hand motor cortex in adults undergoing epilepsy surgery.
Number of Subjects	14
Diagnosis and Main Inclusion Criteria	Patients ages 12-60 years, with planned neurosurgery involving implantation of intracranial subdural electrodes including over the precentral gyrus.
Study Product and Planned Use	Navigated transcranial magnet stimulation (nTMS), Magstim Rapid ² and Brainsight Neuronavigation. Magnetic stimulation will be delivered to hand primary motor cortex, with positive and negative functional sites determined through surface electromyography (EMG).
Reference therapy	N/A
Statistical Methodology	The primary outcome measure will be spatial correlation between topographic maps of hand motor representation obtained through nTMS compared to direct, extra-operative cortical stimulation performed as part of routine clinical care. A secondary outcome measure will be safety and tolerability of TMS in the epilepsy patients.

CONFIDENTIAL

1.1 Background

Surgical treatment of focal epilepsy and motor mapping

Over 30% of epilepsy patients experience recurrent seizures despite the advent of new anti-epileptic medications (Kwan & Brodie 2000). Randomized controlled trials reveal that in appropriately selected surgical populations, epilepsy surgery can achieve superior outcome compared to continued medical therapy (Engel et al 2012).

Patients whose seizure foci are close to the motor cortex remain a challenge due to the potential risk of motor deficits after the surgery. Accurate mapping of the epileptogenic zone and surrounding cortical area is used to guide maximal resection of the epileptogenic cortex while avoiding unacceptable damage to eloquent cortex. **Currently intra-operative direct current stimulation (DCS) is the gold standard, and is the clinical standard of care for surgical planning.** If epileptogenic cortex and putative resection site is close to eloquent cortex. A subdural grid is implanted for intracranial EEG monitoring and seizure foci localization. After enough interictal or ictal events are captured, the patient will have functional mapping while in close monitored EMU setting.¹

However, noninvasive functional mapping of motor cortex, via TMS and other non-invasive modalities such as fMRI or MEG, would optimize presurgical planning and patient counseling. In addition, in some cases, presurgical evaluation could determine whether a surgical resection is feasible, or whether the patient would be a better candidate for another procedure such as responsive neurostimulation (RNS) or vagal nerve stimulation (VNS) which would spare overlapping eloquent cortex. Furthermore in the pediatric epilepsy population, presurgical motor mapping by TMS may determine that motor and other eloquent cortex has completely reorganized (sometimes to the contralateral hemisphere), such that surgical resection of the epileptogenic cortex would be unlikely to cause a functional deficit.

A neurostimulation technique, navigated transcranial magnetic stimulation (nTMS) is a potentially valuable tool for preoperative motor mapping. Previously there have been several studies to test the accuracy of TMS to DCS, and in comparison with other noninvasive modalities, including magnetoencephalography (MEG) and functional MRI (fMRI) (Najib 2011; Romero 2011, Tarapore 2012, Krieg 2012), suggesting that nTMS can have an extremely high degree of functional accuracy, identifying primary motor cortex within 2 mm of accuracy, and with a high positive and negative predictive value (Tarapore 2012).

A similar neuronavigated device, the integrated Nextstim device manufactured by Neurostar, was FDA approved for presurgical motor mapping in 2009 (Please see appendix). We are testing the Magstim Rapid² TMS coil and Brainsight Neuronavigation system (instead of the Nextstim) because the dual system allows co-registration to the patient's structural MRI, functional MRI(fMRI) or EEG. Furthermore,

¹ Electrical stimulation of the cerebral cortex will be conducted utilizing a NicoletOne Cortical Stimulator which delivers a constant current output. The stimulus parameters are set to a pulse width of 500 microseconds, pulse frequency of 50 Hertz and maximum train duration of 5 seconds. The stimulus current is manually controlled during the stimulation and ranged from 1 mA to 12 mA. Stimulation is applied to adjoining electrode pairs. Responses are confirmed with repeat stimulation and testing at the initial pair and with adjoining electrodes when necessary. Electrical stimulation is started at 1 mA and gradually increased in increments of 1-4 mA until a maximum of 12 mA was achieved or until after-discharges are seen or a functional response is observed. Positive and negative functional sites will be recorded.

the dual system is a more flexible system for other research use with other stimulation devices (such as transcranial direct current stimulation and simultaneous EEG recording) and robotic devices.

We propose an open-label feasibility study to test the accuracy of nTMS to the gold standard DCS, as well as to fMRI (an adjunctive presurgical planning tool), in determining both positive and negative motor sites, and correlate with clinical outcomes.

1.2 Investigation device: TMS basics

Application of magnetic pulse for motor cortex stimulation was developed decades ago (Barker 1985). TMS machine consists of a coil which generates a brief, powerful magnetic field. As the current passes through the coil, it generates a magnet field that can penetrate the scalp and skull and in turn induce an electric current in the brain tissue (Kobayashi & Pascual-Leone 2003). When pyramidal neurons of the primary motor cortex are stimulated by electric current, the resultant motor evoked potential (MEP) triggers small movements in the relevant muscle groups, which can then be detected via electromyography (EMG). (Fig 1 adapted from Kobayashi & Pascual-Leone 2003)

[figure not shown]

Fig 1 Principle of TMS: The current flowing briefly in the coil generates a changing magnetic field that induces an electric current in the tissue, in the opposite direction. A motor response can be detected on electromyography when motor cortex is stimulated. (Kobayashi & Pascual-Leone 2003)

TMS can also be integrated with a neuronavigation system, allowing for coregistration with an anatomical scan, such as MRI scan. This navigated TMS (nTMS) system allows for more precise position of coils during the brain stimulation and generate motor maps of high resolution. (Gugino et al., 2001; Julkunen et al., 2009; Kring et al., 2001).

Single pulse and repetitive pulse TMS are both used in neurological research studies and clinical practice. Repetitive TMS can induce lasting changes in cortical excitability and it has been approved for treatment of depression. Single pulse TMS will be used in our study for motor cortex mapping. The practical application of TMS is simple. The TMS stimulation is administered on skull over the motor cortex via the guidance of MRI anatomical scan, surface EMG was applied on individual target muscle (Fig 2, picture adapted from Pitch 2011).

[figure not shown]

Figure 2. Photograph showing the navigated transcranial magnetic stimulation system in use. The stimulator coil is shown placed against the patient's head. The 3D reconstruction of the patient's brain is shown on the computer screen on the top left; the motor evoked potential output tracings are shown on the computer screen on the top right. The image in the bottom right corner shows the surface electrodes for electromyographic monitoring. (Picht et al., 2011).

We will be using the Magstim Rapid², which is a microprocessor-controlled machine which delivers both single and repetitive transcranial magnetic stimulation (TMS). The proposed device is not currently FDA approved for presurgical motor mapping, but is approved for peripheral nerve stimulation (K051864). However, the Nextstim TMS system is currently FDA approved for presurgical motor mapping ([K091457](#)).

Currently, there have been a number of clinical protocols using TMS, which have considered TMS a non-significant risk device.

The TMS device poses a non-significant risk because

1. The device is not an implant with potential for serious risk to health, safety, or welfare of subject.
2. The device is not purported for use supporting or sustaining human life with potential for serious risk to health safety or welfare of subject.
3. The device is not for substantial use in diagnosing, curing, mitigating, or treating disease or otherwise preventing impairment of human health with a potential for serious risk to health safety or welfare of subject.
4. The device does not otherwise present a serious risk to the health safety or welfare of a subject.

We anticipate that this will be a step toward eventual wider application of TMS.

In particular, because TMS will be applied as single pulses to determine motor evoked potentials (MEPs), there will be no modulation of cortical excitability. Single pulse TMS produces monophasic magnetic field pulse of peak amplitude range of 1-2 Tesla is achieved to discharge a capacitor, and is commonly used for research and diagnostic purposes.

In a review by Quintana (2005) of TMS in persons under the age of 18, there were 35 studies using single pulse TMS involving 980 children; with a single seizure reported, even in children with epilepsy or cerebral palsy (which is associated with an increased risk of seizures). In a more recent meta-analysis of data from 165 pediatric subjects from 2009 to 2014, there were no seizures or severe related adverse events reported with single pulse TMS. For these reasons, IRBs at other peer institutions including Cincinnati Children's Hospital, Kennedy-Krieger Institute, Children's Hospital Boston, and University of Pennsylvania and the NINDS have rendered single pulse TMS studies in children minimal risk.

Magnetic fields attenuate rapidly with distance, so it seems unlikely that the fetus might be directly affected by TMS. There are anecdotal reports of pregnant women who underwent successful rTMS

treatment for depression, and no side effects to the child were reported (Nahas et al., 1999; Klirova et al., 2008; Ross 2007). Nevertheless, the effects of the TMS device on the reproductive system (sperm, eggs) or to the developing fetus are unknown. For this reason, pregnant patients will be excluded from participation in this study.

As evidence of safety, the **Nexstim TMS system**, which provides exactly the same type of single TMS described here, is approved for use as a tool to perform mapping of motor cortex in patients with neurological disorders of all ages (December 2009, FDA approval notice K091457), for pre-surgical planning (for example, in epilepsy patients and in brain tumor patients). The Magstim Rapid² is developed and manufactured in accordance with US 21 CFR 820 and is cleared in the USA under 510(k) number K051864 for the stimulation of peripheral nerves. However, unlike the Nexstim system, which is fully integrated with a built in-neuronavigation system, the neuronavigation system (Brainsight) compatible with Magstim permits targeted neuronavigation with MRI layered with fMRI, EEG, or NIRS (near infrared spectroscopy), permitting greater research flexibility and other modalities of validating motor and other eloquent function.

TMS Advantages: In this study, TMS is safe, non-invasive, and offers a potentially useful adjunctive test for presurgical planning. The stimulation coil can be easily placed precisely on interested cortical surface with guidance of anatomical scans. TMS session does not interfere with other treatment or diagnostic tests.

1.3 Clinical Data to Date

Cortical function mapping with TMS has been used and it generates reproducible motor maps in previous research studies. Accurate coil position can be achieved with nTMS and the system achieved an error of less than 3 mm in about 95% of the stimulation (Romero et al., 2011). Evaluation of the physiologic responses, revealed no significant differences between MEP latency, amplitude, and area among sessions in the same subject. In addition, comparing the motor map parameters revealed no significant differences between map area, volume, and amplitude in the 2 mapping sessions (Fig. 3). (Romero et al., 2011; Krieg et al., 2012).

Motor mapping via TMS has been used in planning of surgical resection of brain tumors. Maps of motor system generated with TMS have been demonstrated to correlate well with those generated by MEG and DCS in brain tumor patients (Tarapore et al., 2012; Takahashi 2013). In addition, nMTS mapping studies results in further modification of surgical plans such as leading to more extensive or more restrictive resection in some patients. (Frey et al., 2014; Krieg et al., 2012; Takahashi 2013).

Besides tumor patients, TMS motor cortical mapping can be also used to map motor cortex anatomy in epilepsy patients (Barba et al., 2010; Kamida et al., 2003; Vitikainen et al., 2009 Zsoter 2012), without exacerbating seizure frequency.

[figure not shown]

Fig. 3. Example of interpolated cortical maps of the motor representation for the contralateral FDI muscle in 2 separate mapping sessions. The color scale represents the relative peak-to-peak amplitude of the MEP. The arrow points to the location where the largest averaged peak-to-peak amplitude MEP was elicited (ie, hot spot). The 2 subjects shown underwent 2 mapping sessions (initial session top, second session bottom). No significant differences were observed in motor map parameters between the 2 mapping sessions. (Romero et al., 2011)

1.4 Research Risks & Benefits

1.4.1 Risks of Investigational Devices

Generally TMS is safe and well tolerated in both healthy subjects and neurological patients, as long as general safety recommendations are followed (Wasserman 1998). TMS applied as single pulse mode does not carry the risk of significant magnetic field exposure since the total stimulation time is short, and modulation of cortical excitability is highly unlikely. Single-pulse TMS does not cause any detrimental effects on EEG or cognitive and motor test performance (Bridgers and Delaney, 1989; Bridgers, 1991) and can be safely used in children (Eyre et al., 2001). According to a consensus statement on the safety of TMS (Rossi et al 2009), known side effects of TMS include transient headache (which occurs occasionally), syncope (mostly likely an epiphenomenon instead of relate to direct brain effect, which occurs rarely), local pain (rarely), neck pain (rarely), toothache (rarely) paresthesias (rarely); possible transient hearing changes (rarely) and possible malfunction of electric device only if TMS is delivered in close proximity with devices (rarely) (Rossi 2009). The overall incidence of these mild adverse events are thought to be approximately 5%, with headache being reported as the most common (Maizey 2013). Side effects are transient, and have not been reported to induce permanent neurological changes (Rossi et al 2009, Evans 2007).

The most serious possible side effect of TMS is that of an induced seizure. To date, there have been a total of 16 reports of seizures associated with TMS, of thousands of published studies. Previously the risk of inadvertently induces seizures is estimated to be less than 1 in 1000 rTMS procedures (which is considered a higher risk procedure than single pulse TMS as used in this protocol), a higher risk than most commonly prescribe antidepressants (O'Reardon et al 2005) In a safety review of TMS, Hallet et al (2007) report 3 seizures associated with single-pulse TMS since the 1998 safety guidelines were published for safe stimulation parameters. In first case, Haupt's et al (2004) report a generalized tonic clonic seizure in a patient with multiple sclerosis using single pulse TMS at 66% of TMS output. The authors suggested that the use of olanzapine and the underlying MS likely increased the patient's seizure risk. In the second case, Tharayil et al (2005) reported a generalized seizure in a patient with bipolar

depression taking chlorpromazine and lithium, both medications known to increase seizure risk. To date, there has been a single report of an induced focal motor seizure during single pulse TMS of an epilepsy patient with a known epileptic focus in the left frontal cortex (Classen et al 1995). These few reported seizures were not associated with long term adverse outcome (Schrader et al. 2004).

In the event of a concurrent seizure during stimulation, one or more co-investigators with specialty training in epilepsy will be present to monitor for adverse effects and monitor for exacerbation of seizure type and frequency. If there is immediate cause for concern the PI and Co-PI will make necessary medical arrangements, including direction to the emergency room if needed. If any other unanticipated adverse events occur which are thought to be related to study intervention, the patient will be withdrawn from further participation in the study. Though our clinical trial will include a safety-monitoring plan, there are no known severe or lasting adverse effects with TMS using proper set-up.

1. Though minimal, due to the concern of potential increased seizures with TMS, we will monitor increase in seizure severity attributable to TMS by identifying all instances of generalized tonic clonic seizures after TMS treatments (defined as occurring within 20 minutes of stimulation). In addition, subjects will be asked to keep a seizure diary for the 7 days prior to stimulation, and the 7 days after stimulation. Instances where seizure frequency increased after TMS will be reported to the IRB within 1 week.
2. If a self-limited, short (<5 min) complex partial seizure or evolution into generalized tonic clonic seizures occur during the procedure, TMS mapping will stop for that day.
3. In case of, pain, transient hearing impairment, the patient's primary epileptologist will be notified and appropriate medical followup will be arranged.
4. If any other unanticipated adverse events occur, the patient will be withdrawn from further participation in the study.

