3.1.1 Baseline clinical visit and seizure diary

We will enroll 14 patients who will undergo epilepsy surgery with expected subdural grid coverage over primary motor cortex. Potential subjects will be identified at the weekly multi-disciplinary epilepsy conference. Subjects must have a recent (<2 years) MRI scan, and registration of the TMS coil to the MRI scan via the Brainsight neuronavigation system will be utilized to guide TMS coil placement (Gugino et al 2001). When a presurgical fMRI is available which demonstrates the patient's hand knob, the fMRI will be used with the Brainsight neuronavigation system. Subjects will be recruited and consented during a presurgical clinical visit where the patient's primary epileptologist will introduce members of the research team.

Patients will be asked to keep a 7 day seizure diary prior to the TMS session.

3.1.2 nTMS mapping

Patients will receive a session of single-pulse TMS mapping of the motor area, at the outpatient TMS clinic at NYU Neurology Ambulatory Care Center, at [name] prior their epilepsy surgery, according to the following procedures:

- a. Determination of the motor threshold by (1) finding the most excitable region in the hand knob which elicits the strongest compound muscle action potential (CMAP) in the APB muscle; (2) finding the motor threshold by determining output stimulation intensity which generates peak to peak CMAP response above 50 mV in 5/10 stimulation cycles (Rossini et al., 1994).
- b. Concurrent EMG will be measured with electrodes placed at APB, abductor digiti minimi, flexor carpi radialis muscles. Reference electrode will be placed at the ipsilateral elbow above the brachial biceps muscle.
- c. Mapping of the upper extremity. After determination of the MT, mapping of the UE will be performed at 110% of the rMT. All positive and negative stimulation sites will be recorded and saved.

Patients will be closely monitored during TMS stimulation. Each subject will have a complete neurological examined by a neurologist before and immediately after nTMS. Patients will also be provided a side effects questionnaire after TMS mapping. Patients will then be asked to keep a 7 day seizure diary after the nTMS session

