3.1.3 Follow-up clinical visit after the surgery

After epilepsy surgery patients will receive the standard care for post-operative patients which including close monitoring in ICU overnight. Patients will be transferred to the floor for further clinical evaluation before discharge. Clinical outcome will be evaluated in the post-operative clinic visit within 1 month after discharge. The value of a clinical follow up is to evaluate for any discrepancy between nTMS and DCS, to determine which modality better predicts functional outcome. Any seizure recurrence or neurological deficit will be recorded at the follow-up clinical visit.

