3.3 Secondary Study Endpoints

In addition, this study is designed to detect safety and tolerability of TMS in the epilepsy patient, as measured by 7 day seizure diaries before and after the nTMS sessions.

4 Subject Selection and Withdrawal

We will recruit 14 patients, aged 12-60 years, who will have motor mapping and epilepsy surgery. Because nTMS is expected to most benefit pediatric patients, we plan to enroll at least 4 subjects under the age of 17, to establish validity in this population. There will be no restrictions on race or ethnicity.

Safety and tolerability in healthy volunteers is established for TMS in previous studies, and therefore healthy controls will not be necessary. However side effect questionnaire will be provided after TMS mapping.

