8.1 Definitions

Unanticipated Problems Involving Risk to Subjects or Others

Any incident, experience, or outcome that meets all of the following criteria:

- Unexpected in nature, severity, or frequency (i.e. not described in study-related documents such as the IRB-approved protocol or consent form, the investigators brochure, etc)
- Related or possibly related to participation in the research (i.e. possibly related means there is a reasonable possibility that the incident experience, or outcome may have been caused by the procedures involved in the research)
- Suggests that the research places subjects or others at greater risk of harm (including physical, psychological, economic, or social harm).

Unanticipated Adverse Device Effect

An Unanticipated Device Effect is any serious adverse effect on health or safety, or any life-threatening problem or death caused by, or associated with a device, if that effect, problem, or death was not previously identified in nature, severity, or degree of incidence in the investigational plan or application (including a supplementary plan or application), or any other unanticipated serious problem associated with a device that relates to the rights, safety, or welfare of subjects.

Serious injury

Any injury or illness that is any one of the following:

- life-threatening
- results in permanent impairment of a body function or permanent damage to body structure
- necessitates medical or surgical intervention to preclude permanent impairment of a body function or permanent damage to a body structure

Adverse Event

(a) In parallel with recording the primary outcome, we will monitor for increase in seizure severity attributable to TMS by identifying all instances of generalized tonic clonic seizures after TMS treatments. Instances where seizure frequency increased after TMS will be reported to the IRB within 72 hours.

(b) If a self-limited, short (<5 min) partial seizure or evolution into generalized tonic clonic seizure occur, TMS mapping will stop for that day.

(c) If a secondarily generalized (convulsion starting in one area of body and then spreading to other areas) or 2 partial seizures occur during treatment, the patient will be withdrawn from further participation in the study.

(d) If any other unanticipated adverse events occur, the patient will be withdrawn from further participation in the study.

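### Read as written, withdrawal after a qualifying seizure or an unanticipated event takes the patient off the whole study, not only nTMS, and so ends the post-session seizure diary that measures safety

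*Combined protocol and SAP*

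**What the plan says.** Four sentences in the combined protocol and SAP share one consequence.

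- Section 1.4.1, running text, on other unanticipated events: "which are thought to be related to study intervention, the patient will be withdrawn from further participation in the study".
- Section 1.4.1, item 4 of the closing list: the same consequence, without the condition that the event be related.
- Section 8.1(d), also without that condition: "If any other unanticipated adverse events occur, the patient will be withdrawn from further participation in the study".
- Section 8.1(c), for a secondarily generalized seizure: "or 2 partial seizures occur during treatment, the patient will be withdrawn from further participation in the study".

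A lesser consequence also exists. Section 8.1(b), for a short self-limited seizure, reads: "partial seizure or evolution into generalized tonic clonic seizure occur, TMS mapping will stop for that day". Item 2 of 1.4.1 is close to it.

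On exposure, 3.1.2 says: "Patients will receive a session of single-pulse TMS mapping of the motor area". The phase table in 3.1 and the visit description in 6.2 also show one session. Section 3.3 defines safety and tolerability "as measured by 7 day seizure diaries before and after the nTMS sessions". The post-operative visit in 3.1.3 serves "to determine which modality better predicts functional outcome", and 6.3 adds a hand questionnaire there.

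Section 4.4.1 does not list adverse events among its grounds for withdrawal and states no follow-up for withdrawn patients. Section 8.2 has each adverse device effect followed until it resolves, stabilizes or is judged not caused by the study. Section 9.1 mentions vital status after a patient revokes authorization.

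**The concern.** Stopping an intervention and leaving a study are different acts, and these sentences merge them. With a single session, the nTMS exposure is over or can be halted when the trigger occurs. What remains is the diary, follow-up of the event, routine surgery and DCS, and the 1-month visit. None of these delivers further TMS, so leaving the study adds no protection from the device.

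The cost falls on the safety endpoint. A patient withdrawn under 8.1(c) has just had serious seizure activity during mapping and, on the plain reading, then has no post-session diary. The before/after comparison is missing because of the outcome it is meant to detect. The diary also supports oversight: item 1 of 1.4.1 and 8.1(a) require a rise in seizure frequency after TMS to be reported to the IRB, and 8.4 names such a rise as a possible reason to pause the study. The diary is the structured record described for seeing it.

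**Working it through.** **Step 1. Plan figure used.** Enrolment is 14 (7.1): 10 plus about one third, 10 × 4/3 = 13.3, rounded up to 14. Section 7.1 gives side effects and seizures among the reasons for the extra patients. Extra patients replace numbers; they do not correct a loss that depends on the outcome.

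**Step 2. The rules side by side.**

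| Event | Where | Consequence |
|---|---|---|
| One short, self-limited partial seizure | 8.1(b); 1.4.1 item 2 | Mapping stops for the day |
| Partial seizure that evolves to generalized tonic clonic | 8.1(b); 1.4.1 item 2 | Mapping stops for the day |
| Secondarily generalized seizure | 8.1(c) | Leaves the study |
| Two partial seizures during treatment | 8.1(c) | Leaves the study |
| Other unanticipated event, related | 1.4.1 running text | Leaves the study |
| Other unanticipated event, any cause | 1.4.1 item 4; 8.1(d) | Leaves the study |

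Rows 2 and 3 overlap and give different answers. Row 1 makes row 4 hard to reach: after one short partial seizure mapping stops, so a second must come before it has stopped, or the first was not short and self-limited.

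**Step 3. Loss per withdrawn patient.** Withdrawal during the session loses 7 of 7 post-session diary days, so that patient has no before/after pair: 1/14 = 7.1% of pairs. If the patient is one of the planned minimum of 4 children (7.1), it is 1/4 = 25% of that minimum. Withdrawal later in the diary week loses fewer days.

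**Step 4. Chance of at least one trigger in 14 patients.** The formula is 1 − (1 − p)^14, with p the per-patient probability. The documents give no rate for this population. The nearest figure, in 1.4.1, is below 1 in 1000 rTMS procedures; the protocol regards rTMS as riskier than single pulse.

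| p | Source | Chance of at least one |
|---|---|---|
| 0.001 | rTMS figure, 1.4.1 | 1 − 0.999^14 = 1.4% |
| 0.01 | assumed | 1 − 0.99^14 = 13.1% |
| 0.02 | assumed | 1 − 0.98^14 = 24.6% |
| 0.05 | assumed | 1 − 0.95^14 = 51.2% |

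The first row concerns induced seizures. Section 8.1(c) counts any seizure of its kind during treatment, including a spontaneous one, and the unanticipated-event sentences cover other events, so 1.4% is a reference point and not a bound.

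**Step 5. Illustration, all counts assumed.** Suppose one patient has a secondarily generalized seizure in the session, would have recorded a rise in the diary, and nobody else does. With follow-up the diary result is 1/14 = 7.1% (exact two-sided 95% CI 0.2% to 33.9%). With withdrawal it is 0/13 = 0% (0% to 24.7%). The diary then looks clean, although the in-session seizure is still on record as an event.

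**The case against.** The best reply is that the end of the diary is inferred. Item 1 of 1.4.1 asks for a diary in the week after stimulation and makes no exception for withdrawn patients, and 8.1(a) wants every generalized tonic clonic seizure after TMS identified. Beside a rule that stops mapping for the day, 8.1(c) could mean only that the patient does not return for mapping. That reading is possible. But the sentences speak of the study, the authors used narrower words in 8.1(b), and no section keeps a withdrawn patient on the diary. Two readings of a safety rule are themselves a reason to reword it.

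It is also fair that the damage is limited. Section 8.2 keeps the event recorded and followed, and the same-day examination and side-effects questionnaire (3.1.2) remain. Section 7.2 specifies no diary analysis, so no planned test is biased. Headache, syncope, pain, hearing change and seizure are already described as known effects, which narrows the unanticipated category. All of this stands and bears on size. However, 8.2 follows an event to resolution; it does not ask for seizure counts over the next 7 days against baseline.

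A reader might infer more than the documents support:

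- That any in-session seizure ends follow-up. It does not: a single short partial seizure only stops mapping for the day.
- That the primary analysis is affected. Section 7.3 turns on completing mapping and later having DCS, not on remaining in the study.
- That the hand questionnaire is lost safety data. It measures function after surgery and is not an endpoint in 3.2 or 3.3.
- That 1.4.2 discards these patients' data. Its sentence concerns a patient who withdraws and does not clearly reach withdrawal by the investigator.
- That the unanticipated-event trigger should be limited to related events. The sentences do differ on this, but the wider trigger is a cautious stop in a study enrolling from age 12, and narrowing it is a debatable trade-off.

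**Conclusion.** The point holds in limited form. As written, 8.1(c) and the three unanticipated-event sentences end study follow-up where stopping nTMS would protect the patient equally well. The main loss is the post-session diary, and it is selected on the safety outcome: 7.1% of before/after pairs for each in-session withdrawal. The event is likely to be rare, about 1.4% across 14 patients at the rTMS figure; anything higher rests on assumed rates. The conclusion assumes that leaving the study ends the diary, which is the plain reading and is not contradicted, and that no second session is planned. If a repeat session were intended, a rule of no further nTMS would cover it. Separately, 8.1(b) and 1.4.1 item 2 conflict with 8.1(c) on a seizure that generalizes. This should be corrected because the correction is cheap, not because it threatens the main result.

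**What to change.** 1. In the 1.4.1 running text, 1.4.1 item 4, 8.1(c) and 8.1(d), replace the withdrawal clause with: *no further nTMS; the post-session diary, adverse-event follow-up and 1-month visit continue unless the patient (or parent/guardian) withdraws permission*.
2. Align 8.1(b) and 1.4.1 item 2 with 8.1(c), so that a seizure that generalizes always means no further nTMS.
3. State in 1.4.2 that the discard of PHI does not apply when the investigator stops nTMS.
4. Leave the relatedness conditions of item 4 and 8.1(d) as they are.

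The cost is a small protocol amendment with IRB review, and matching consent and assent wording if needed; those pages were not available to check. No procedure, visit or patient is added: the patients concerned complete a diary and questionnaire already planned for them, and may decline.
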